5.4 Physical Examinations

Physical examination dates will be listed.

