6.3 Physical and Neurological Examinations

6.3.1 Physical Examination

The physical examination include assessments of general appearance, skin, head (eyes, ears, nose, and throat), neck, thyroid, lungs, heart, abdomen, back, lymph nodes, and extremities, and body weight will be performed during [REDACTED] by the principal investigator or subinvestigator. A limited examination to assess clinically significant changes from the examination performed at screening will be completed during the [REDACTED] visit. Height will only be obtained at screening.

The physical examination will also include visual acuity and dilated ophthalmoscopy (by an ophthalmologist) and with OCT (where available) at screening and [REDACTED] visit to rule out and monitor for any significant retinal disease, including macular edema. Retinal photos will be taken during the screening visit [REDACTED] visit and any subsequent unscheduled ophthalmoscopy.

Safety ECGs will also be performed as outlined in the schedule of procedures and visits (██████).

Clinically significant findings from the physical/neurological examination performed at screening will be recorded as medical history. Any new clinically significant findings from the time of screening through the first dose of study drug will be recorded as pre-treatment AEs. After the administration of the first dose of study drug, clinically significant findings will be recorded as AEs.

[figure not shown]

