9.8.2 Physical Examinations

Physical examination results (abnormalities only) at each study visit will be listed.

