2 DEMOGRAPHIC AND OTHER BASELINE CHARACTERISTICS

All baseline patient characteristics of demographic data (age, height, and weight), ulcerative colitis history, social history, medical history (abnormalities only), physical examination (abnormalities only), and concomitant medications at study entry will be listed for all patients. Demographic and baseline characteristics of the safety population will be summarized by treatment group and for the overall population. Baseline for the demographic variables will be the last pre-randomization value collected at the screening visit. Continuous variables will be summarized using number of values (n), mean, standard deviation (SD), median, minimum, and maximum. Frequencies and percentages will be reported for all categorical data. No formal statistical testing comparing treatment groups will be performed.

The following variables will be summarized by treatment group:

1. Continuous baseline demographic variables: age (years).
2. Categorical baseline demographic variables: sex (female or male), race (American Indian or Alaska Native, Asian, Black or African-American, Native Hawaiian or Other Pacific Islander, White or Caucasian, or Other) and ethnicity (Hispanic or Latino, Not Hispanic or Latino).
3. Ulcerative colitis history which include:
 - Duration of Ulcerative Colitis (in years)
 - Disease localization (Proctosigmoiditis/Left sided colitis, Pancolitis/ Extensive colitis)
 - Presence or absence of current oral corticosteroid usage at baseline
 - Inadequate responders/Lost response and/or Intolerant to corticosteroid (including duration of treatment)
 - Previous exposure to TNF α antagonists (including duration of treatment)
 - Inadequate responders/Lost response and/or Intolerant to TNF α antagonists
 - Previous exposure to immunosuppressives (including duration of treatment)
 - Inadequate responders/Lost response and/or Intolerant to immunosuppressives
 - Previous use of integrin antagonist (including duration of treatment) and response
 - Previous use of oral 5-aminosalicylates (including duration of treatment) and response
 - Baseline Disease Activity (Mayo Clinic Scores)

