5.3 Adverse Events

Adverse events will be coded using the most current Medical Dictionary for Drug Regulatory Affairs (MedDRA, version 18.0 or later) and tabulated, including categorical information of interest such as onset and resolution times, time of onset relative to dose, severity at onset, maximum severity, causal relationship to study medication, and action taken. AEs will be regarded as ‘pre-treatment’ if they occur between screening and the time of administration of the first dose of APD334 or placebo and will be recorded as medical history. All other AEs that occur after the first dose of study medication will be considered to be ‘treatment-emergent’.

Treatment-emergent AEs (TEAE) will be listed by patient and by treatment. They will be summarized per treatment and expressed in terms of maximum severity and relationship to study medication. The incidence of TEAEs classified according to system organ class (SOC) will be summarized by treatment group. TEAEs will also be summarized by maximum intensity (assessed according to the Common Terminology Criteria for Adverse Events v4.03⁸ definitions) and relatedness to study medication.

Summaries of the number (%) of patients in each treatment group with at least 1 TEAE, classified according to MedDRA system organ class and preferred term, will also be provided for:

- Drug-related TEAE
- Treatment-emergent AEs leading to permanent discontinuation of study medication (study medication discontinued or withdrawal from study).
- Serious adverse events (SAEs)

Serious adverse events will be listed by patient and by treatment. If there are no SAEs at the end of the study, the tables or listings will state that there are no SAEs in the study.

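### SAP 5.4 cuts the protocol's by-visit listing of abnormal physical examination results to a list of dates, so on-treatment abnormalities not recorded as adverse events go unlisted

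*SAP*

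**What the plan says.** Protocol 9.8.2 sets the output for physical examinations: "Physical examination results (abnormalities only) at each study visit will be listed". The whole of SAP 5.4 reads: "Physical examination dates will be listed".

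At baseline the two documents agree. SAP Section 2, like Protocol 9.4, keeps abnormal findings at entry: "physical examination (abnormalities only), and concomitant medications at study entry will be listed for all patients".

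Protocol 6.3.1 makes visual acuity, dilated ophthalmoscopy and, where available, OCT part of the physical examination. Their stated purpose is "to rule out and monitor for any significant retinal disease, including macular edema". The same section sets the route for findings made on treatment: "After the administration of the first dose of study drug, clinically significant findings will be recorded as AEs". SAP 5.3 then reports those events: "Treatment-emergent AEs (TEAE) will be listed by patient and by treatment". It also summarizes them by system organ class, severity and relatedness.

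**The concern.** A date shows that an examination took place, not what it found. The SAP therefore shows abnormalities at entry with no on-treatment counterpart, although the protocol promised both.

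The protocol synopsis puts physical examination, with ophthalmoscopy and OCT, first among the safety assessments, and Protocol 6.3.1 names a retinal risk that it is meant to detect. If results are not listed, a reader of the report depends on the adverse event record alone. That reader cannot see lesser abnormalities, and cannot tell whether an abnormal examination that should have produced an adverse event did so.

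**Working it through.** No figure in the plan bears on this point, so the check compares the texts and follows each kind of finding to the place where it would be reported.

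1. **On-treatment output.** Protocol 9.8.2 gives abnormal results by visit; SAP 5.4 gives dates. None of the result content survives in 5.4.

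2. **Baseline output.** Protocol 9.4 and SAP Section 2 both list abnormalities at study entry. Only the on-treatment part has changed.

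3. **Neighbouring sections.** SAP 5.5 (concomitant medication), 5.6 (vital signs) and 5.7 (laboratory values) keep the listings and summaries of Protocol 9.8.3 to 9.8.5, and 5.5 adds a tabulation. Of these four short sections, 5.4 is the only one that drops an output.

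4. **Declaration.** SAP 1.1 points to Section 9 for changes from the protocol. The readable text of Section 9 covers endpoints, sample size, confidence level, the remission and response definitions, and multiple imputation. It has no entry on physical examinations. Parts of it are redacted.

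5. **Where a post-dose abnormality goes under the SAP.**
   - Recorded as an adverse event: it appears in the treatment-emergent listings and tables of SAP 5.3. It is not lost.
   - Present at entry and unchanged: the entry listing shows it, but its on-treatment status is not listed.
   - New or changed, but not recorded as an adverse event: Protocol 9.8.2 would list it; no readable part of the SAP does.

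   The second and third groups are the loss, together with the comparison of examination results with the adverse event record.

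6. **Eye examinations.** Because Protocol 6.3.1 places them inside the physical examination, Protocol 9.8.2 covers their abnormal results, and SAP 5.4 covers only their dates. No separate output for them is legible in the SAP. However, the SAP contents list has a redacted entry after 5.8, and the body of 5.8 is not readable.

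7. **How many examinations.** In the readable procedure lists of Protocol 7.4, the Day 1 examination is a limited update of screening. The list for the intermediate visits has no physical examination. The final list, with the Week 12 endoscopy, has one, including ophthalmoscopy, OCT and retinal photographs. As far as can be read, that is about one scheduled post-dose examination per patient; Protocol 6.3.1 also provides for unscheduled ophthalmoscopy. The schedule table is redacted, so this count is provisional.

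**The case against.** The strongest reply is that the adverse event route already does the work. Protocol 6.3.1 sends clinically significant post-dose findings there, and the definition in Protocol 6.11.1 is broader still, taking in objective signs and the worsening of existing conditions. A case of macular edema would be expected in the SAP 5.3 tables. This stands, and it limits the point. A reader might infer from SAP 5.4 that on-treatment findings, macular edema included, vanish from the safety report; the documents do not support that.

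It does not remove the point. The protocol provides for adverse event reporting in 9.8.1 and for the results listing in 9.8.2, so it did not treat the first as a substitute for the second. A listing of results is also what allows the adverse event record to be checked.

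Three further replies deserve weight:

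- **Protocol Section 9 is described as an overview, with detail left to the SAP.** True, but replacing results with dates takes content away; it does not fill in detail.
- **Redactions could hide a separate retinal output or a declared change.** This stands. The mismatch between 5.4 and 9.8.2 is certain; the absence of any retinal output is not.
- **The protocol promised only a listing.** This also stands. A display paired with baseline, or a count by arm of new retinal abnormalities, goes beyond what Protocol 9.8.2 offered, and the SAP cannot be faulted for lacking either.

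**Conclusion.** The point holds as a minor one. SAP 5.4 reduces a protocol safety listing to dates, and the readable SAP neither declares nor explains this. The loss is on-treatment abnormalities not recorded as adverse events, and the check of examination results, eye findings included, against the adverse event record. No efficacy conclusion is affected, nor any adverse event, laboratory, vital sign or ECG output.

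No percentage should be attached. A reader might be tempted to set one or two findings against the roughly 39 patients per group in SAP 7.1. Those are patients with the Mayo score at baseline and Week 12, whereas SAP 5.1 bases safety outputs on all randomized patients who were dosed. The documents also give no rate for examination abnormalities that fall short of an adverse event.

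The conclusion rests on two assumptions: that the redacted text does not already declare the change or report the eye results, and that post-baseline examination results are captured at all. The documents do not show the case report form, so the second cannot be confirmed.

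**What to change.** Replace SAP 5.4 with the Protocol 9.8.2 rule: list abnormal physical examination results by patient, treatment and visit. State that this covers the visual acuity, ophthalmoscopy and OCT findings of Protocol 6.3.1, or cross-refer to the SAP section that already reports them.

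If the database holds only dates after baseline, keep 5.4, but declare the change in SAP Section 9 with the reason and state that post-dose findings are reported through the adverse event outputs of 5.3.

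A count by arm of patients with a new retinal abnormality would be a useful addition, but it is optional.

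The cost is one SAP paragraph and one listing, drawn from examinations already scheduled. No new assessment is needed.

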5.5 Concomitant Medication

Pre-treatment and concomitant medication administered during the study will be listed. Concomitant medications will be coded using the World Health Organization Drug Dictionary (WHODRUG Dictionary) and will be tabulated by drug class and preferred term.

5.6 Vital Signs

[figure not shown]
Individual vital sign measurements will be listed by treatment and summarized using descriptive statistics. Summary statistics will also be provided for change from baseline in vital sign measurements by treatment. If Day 1 pre-dose assessment is completed then this will be used for baseline. If the Day 1 pre-dose assessment is missing, then the last non-missing assessment prior to randomization will be used.

[figure not shown]
5.7 Clinical Laboratory Values

Individual lab values will be listed by treatment and visit, and summarized using descriptive statistics. Summary statistics will also be provided for change from baseline in lab values. Shift tables from baseline to last double-blind visit will also be produced for the laboratory assessments based on the categories of Low, Normal, and High. Baseline is defined as the last value of a specific endpoint measured before first dose of study medication.

If any laboratory value falls above or below the upper or lower level of quantification, the value of the upper or lower level of quantification will be taken (e.g. <0.2 will become 0.2) for summaries but left as recorded in the listing.

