5.8.2 Blinding

The sponsor, patients, and personnel involved with the conduct of the study, with the exception of the clinical supply staff, safety staff, and the unblinded statistician supporting the Data Safety Monitoring Board (DSMB), will be blinded to the identity of study medication.

In addition, the sponsor, patients, and personnel involved with the conduct of the study will also be blinded to the total WBC and [REDACTED], as access to this information may

lead to unintentional unblinding of a patient (due to Investigational Product's mechanism of action). A central CRO physician(s) unblinded to the [REDACTED] and leucocyte counts, but blinded to the study medication, will review and monitor the total WBC and [REDACTED] counts for safety purposes in the trial. The study site personnel will not receive laboratory results for the total WBC or [REDACTED].

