6.11.1 Adverse Event Reporting

Patients will be instructed that they may report AEs at any time. AEs that occur from ICF signature until the time of administration of the first dose of APD334 will be regarded as ‘pre-treatment’ and recorded as an AE. All events reported following study medication administration up to 30 days after the last medication intake will be presented as treatment emergent AEs (TEAEs)

Monitoring of AEs will be continued up to 30 days after study medication administration. In the event that an AE is not resolved or stabilized by this time, the sponsor in consultation with the investigator will decide whether to continue to monitor the AE or close-out the event in the database if no further follow-up is necessary.

For this study, an AE is defined as: “Any untoward medical occurrence in a study patient administered any dose of study medication (APD334 or placebo) and which does not necessarily have to have a causal relationship with this treatment.” An AE can therefore be any unfavorable and unintended sign (including an abnormal laboratory finding), symptom, or disease temporally associated with the use of the study medication, whether or not related to the product. AEs can be any of the following:

- Unfavorable changes in general condition
- Subjective or objective signs/symptoms

- Concomitant disease or accidents
- Clinically relevant adverse changes in laboratory parameters observed in a patient in the course of a clinical study
- Pre-existing conditions which worsen in severity or frequency or which have new signs/symptoms associated with them

Lymphopenia will not be captured as an adverse event both to maintain the study blind, and also because it is an expected pharmacologic effect of the drug. In order to ensure safe conduct of the study and minimize the risk of study personnel or sponsor becoming unblinded to treatment assignment, total WBC and [REDACTED] will be monitored by a central CRO physician(s) unblinded to the [REDACTED] and leucocyte counts. This person will remain blinded to the study medication

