9.8.5 Clinical Laboratory Values

Individual lab values will be listed by treatment and visit, and summarized using descriptive statistics. Summary statistics will also be provided for change from baseline in lab values. Baseline is defined as the last pre-randomization measurement. Shift tables from baseline to last double-blind visit will also be produced for the laboratory assessments based on the categories of Low, Normal, and High. A clinically significant change from baseline may be recorded as an AE if deemed appropriate by the PI or sponsor.

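### The only readable laboratory table that counts patients by category stops at the last visit in Low/Normal/High, so transient abnormalities and depth are not counted by arm; the gap matters most for white cells

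*SAP*

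**What the plan says.** Laboratory analysis is described in SAP 5.7 and Protocol 9.8.5, and the two agree. The protocol reads: "Shift tables from baseline to last double-blind visit will also be produced for the laboratory assessments based on the categories of Low, Normal, and High". SAP 5.7 uses the same comparison, "Shift tables from baseline to last double-blind visit will also be produced for the laboratory assessments", and the same classes, "based on the categories of Low, Normal, and High".

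SAP 5.7 also plans two other outputs: "Individual lab values will be listed by treatment and visit, and summarized using descriptive statistics", and "Summary statistics will also be provided for change from baseline in lab values". SAP 5 names the statistics for safety summaries: N, mean or median, SD, and change or percent change, with 90% confidence intervals for differences between groups. It names no worst value, nadir or toxicity grade.

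Two protocol rules bear on white cells. Section 6.11.1 states: "Lymphopenia will not be captured as an adverse event both to maintain the study blind"; its second reason is that the effect is expected from the drug's pharmacology. Section 5.8.2 states that "the sponsor, patients, and personnel involved with the conduct of the study will also be blinded to the total WBC" and to a further, redacted, item. For laboratory changes in general, Protocol 9.8.5 says: "A clinically significant change from baseline may be recorded as an AE if deemed appropriate by the PI or sponsor".

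**The concern.** The safety objective is to describe the safety profile in a study that compares two doses with placebo. For laboratory data the natural question is how many patients in each arm became abnormal on treatment, and how badly. The planned table answers a different one: how many were outside the reference range at the end.

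Two kinds of patient are affected. One is abnormal at a mid-treatment visit and back in range at the last visit, and is tabulated as Normal to Normal. The other falls far below the lower limit, and is tabulated exactly like a patient just below it.

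For most parameters the AE tables can partly fill this gap. For lymphocytes they cannot, by rule. For total WBC, the sponsor and study personnel who would judge a change clinically significant do not see the result. At stake is whether the study report can give, by dose, the number of patients with marked white-cell lowering.

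**Working it through.** No figure in the plan is in dispute, so the main check is which readable output would show each kind of patient.

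| Planned output | Abnormal mid-treatment, normal at last visit | Depth within Low or High |
|---|---|---|
| Shift table (SAP 5.7, Protocol 9.8.5) | Normal to Normal | Not shown |
| By-visit and change summaries (SAP 5, 5.7) | Contributes to that visit's average; no patient count | On average by arm; no patient count |
| Listings (SAP 5.7) | Shown, not counted | Shown, not counted |
| TEAE tables by maximum severity (SAP 5.3), not lymphopenia | If judged an AE | By CTCAE grade, if judged an AE |
| TEAE tables, lymphopenia | Excluded by Protocol 6.11.1 | Excluded by Protocol 6.11.1 |

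Three details limit what the by-visit summaries can add.

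- If descriptive statistics include minimum and maximum, as SAP 2 specifies for baseline variables, the reader sees one extreme in each direction per arm and visit, still not a count.
- SAP 5.1 imputes no missing safety data, so a patient who leaves drops out of later by-visit averages.
- SAP 8.2 keeps the assessment closest to the target date when a window holds more than one. If that rule covers laboratory tests, an unscheduled test can be left out of the summary.

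The plan is also uneven: SAP 5.3 summarises adverse events by maximum severity, while SAP 5.7 classes laboratory values by the last one.

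**Illustration of size (assumed inputs).** The laboratory schedule is redacted. SAP 7.4.1 gives Weeks 1, 2, 4, 8 and 12 as post-baseline time points for imputation, so take V = 5 tests, and V = 4 as a variant. Assume one abnormal run of k consecutive tests, equally likely to start at any feasible visit. There are V − k + 1 possible starts, and only one covers the last visit, so P(missed) = 1 − 1/(V − k + 1).

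| k | V = 5 | V = 4 |
|---|---|---|
| 1 | 1 − 1/5 = 80% | 1 − 1/4 = 75% |
| 2 | 1 − 1/4 = 75% | 1 − 1/3 = 67% |
| 3 | 1 − 1/3 = 67% | 1 − 1/2 = 50% |
| 4 | 1 − 1/2 = 50% | 0% |
| 5 | 0% | – |

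To put this in patients, use about 39 per arm (the evaluable number in SAP 7.1, used only for scale) and V = 5. Expected number missed = 39 × incidence × P(missed):

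| Assumed incidence | k = 1 | k = 2 | k = 3 |
|---|---|---|---|
| 5% | 1.56 | 1.46 | 1.30 |
| 10% | 3.12 | 2.93 | 2.60 |
| 20% | 6.24 | 5.85 | 5.20 |

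The extreme case is true by construction: if 4 of 40 patients (10%) have a rise that resolves before exit in all four, the shift table shows 0 of 40. That is an assumption for illustration, not a figure from the documents.

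Depth needs no arithmetic. Any fall from Normal to below the limit reads Normal to Low, and any further fall from a Low baseline reads Low to Low.

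**The case against.** The strongest reply is that the shift table is one output among several, and a good deal of this reply stands.

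- **The doses can be compared on depth.** SAP 5 plans mean or median change and percent change with between-group 90% confidence intervals, and Protocol 6.8.1 includes WBC with absolute differential counts. A reader might infer that the plan cannot separate the doses on white-cell lowering. That is true of the shift table only; average lowering can be compared.
- **Abnormal patients are not hidden.** Every value is listed. Protocol 6.8 asks the physician to judge whether an abnormal result is an AE, 6.11.1 counts abnormal laboratory findings as possible AEs, and SAP 5.3 tabulates TEAEs by maximum severity and those leading to discontinuation. A patient stopped for raised ALT would be expected there. Capture still depends on judgment, and the route is closed for lymphopenia.
- **Early stoppers may be caught.** Protocol 6.13.1 asks for the exit procedures at premature discontinuation, so the last visit may fall close to the event. This does not help with patients who recover while continuing or after resuming.
- **Persistent lowering still shows as Low.** It does, without depth.
- **Counts are watched during the trial.** A central physician monitors them and the DSMB sees unblinded reports. That protects patients, but does not produce a by-arm summary for the study report.
- **Redaction.** The text of SAP 5.8 is not shown, a contents entry after it is redacted, SAP numbering jumps from 4.3.3 to 4.5, Protocol numbering jumps from 9.6.5 to 9.8, and contents entries after Protocol 9.8.5 are blank. A separate hematology analysis may exist, so none can be called missing. It would not settle the point for ALT, AST or other chemistry unless it covers them too.

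**Conclusion.** The point holds as a limited gap in summary reporting, and the fix is a cheap improvement. In the readable text, no table counts patients by arm by worst on-treatment laboratory value or by laboratory toxicity grade. The SAP and protocol agree on this, so there is no contradiction to resolve.

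A reader might go further and infer that mid-treatment toxicity does not appear in the reporting at all, or that listings are its only source. The documents do not support either: listings, by-visit and change summaries, and AE tables for everything but lymphopenia all carry part of the information.

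The gap matters most for white-cell parameters, because lymphopenia cannot become an AE and total WBC is withheld from the sponsor and study personnel. This part depends on what the redacted sections contain. The size cannot be taken from the documents. The range of 67% to 80% missed, for runs of one to three visits out of five, rests on an assumed schedule and random placement; with four visits it is 50% to 75%. A run that lasts through the final visit is not missed.

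**What to change.** In SAP 5.7:

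1. Add a shift table from baseline to the worst post-baseline on-treatment value, separately for the lowest and the highest value, with unscheduled tests included. State where the on-treatment period ends.
2. Add counts of patients by maximum CTCAE v4.03 grade, by arm, for gradable parameters, including lymphocytes, WBC, ALT and AST. SAP 5.3 already uses this version for adverse events.
3. Keep the planned last-visit Low/Normal/High shift alongside.
4. Produce the new tables from the laboratory data after unblinding, so that the blind and the AE rule in Protocol 6.11.1 are untouched.
5. Cross-refer to any existing hematology analysis, so that the white-cell tables are not duplicated.

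The cost is SAP wording and a few extra tables from data already collected. Worst-value tables will show higher abnormality rates in every arm, placebo included, so they should be read as comparisons between arms.
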